## LIST OF ABBREVIATIONS

Abbreviation	Term
[REDACTED]	[REDACTED]
6MWT	6-minute walk test
AE	adverse event
AIHA	autoimmune hemolytic anemia
BMI	body mass index
[REDACTED]	[REDACTED]
CRF	case report form
CTCAE	Common Terminology Criteria for Adverse Events
ECG	electrocardiogram
eCRF	electronic case report form
FACIT-F	Functional Assessment of Chronic Illness Therapy - Fatigue
MedDRA	Medical Dictionary for Regulatory Activities
PD	pharmacodynamic
[REDACTED]	[REDACTED]
[REDACTED]	[REDACTED]
Pi3K	phosphoinositide 3-kinase
[REDACTED]	[REDACTED]
PT	preferred term
QD	once daily
QTcF	Fridericia's correction
SAP	statistical analysis plan
SOC	system organ class
TEAE	treatment-emergent adverse event
ULN	upper limit of normal
[REDACTED]	[REDACTED]
wAIHA	warm autoimmune hemolytic anemia
[REDACTED]	[REDACTED]
WHO	World Health Organization

## 1. INTRODUCTION

This is a Phase 3, multicenter, randomized, double-blind, placebo-controlled study to evaluate the efficacy and safety of parsaclisib 2.5 mg QD compared with placebo over a 24-week double-blind treatment period followed by a 24-week open-label treatment period of parsaclisib. Participants may then continue to receive parsaclisib in a long-term extension period.

On 17 APR 2023, Incyte decided to terminate this Phase 3 study. The decision was based on the change in the regulatory landscape for Pi3k-delta inhibitors combined with enrollment challenges. At the time of this decision, 13 participants had been randomized and received study drug in this study.

The purpose of this SAP is to provide details of the statistical analyses that have been outlined in the INCB 50465-309 Protocol. The scope of this plan includes the final analyses, which will be executed by the Department of Biostatistics or designee.

## 2. STUDY INFORMATION, OBJECTIVES, AND ENDPOINTS

### 2.1. Protocol and Case Report Form Version

This SAP is based on INCB 50465-309 Protocol Amendment 2 dated 10 MAY 2023 and CRF approved 27 APR 2023. Unless superseded by an amendment, this SAP will be effective for all subsequent Protocol amendments and eCRF versions.

### 2.2. Objectives and Endpoints

[Table 1](#) presents the objectives and endpoints.

**Table 1: Objectives and Endpoints**

Objectives	Endpoints
Primary	
To evaluate the efficacy of parsaclisib in the treatment of participants with wAIHA.	Proportion of participants attaining a durable hemoglobin response, defined as hemoglobin $\geq 10$ g/dL with an increase from baseline of $\geq 2$ g/dL not attributed to rescue therapy at $\geq 3$ of the 4 available visits at Week 12 and/or later during the 24-week double-blind treatment period.
Key Secondary	
To further evaluate the efficacy of parsaclisib in the treatment of participants with wAIHA.	Proportion of participants with a $\geq 3$ -point increase from baseline in FACIT-F score at Week 24.

**Table 1: Objectives and Endpoints (Continued)**

Objectives	Endpoints
Other Secondary	
To further evaluate the efficacy of parsaclisib in the treatment of participants with wAIHA.	

• Proportion of participants with a 50 m increase from baseline to Week 24 in a 6MWT.

• Change and percent change from baseline in FACIT-F score at each postbaseline visit.

• Change and percentage change from baseline in hemoglobin at each postbaseline visit.

• Proportion of participants who received transfusions from Week 6 to Week 24 and from Week 24 to Week 48.

• Change and percentage change from baseline in daily corticosteroid dose at Week 24.

• Proportion of participants who required rescue therapy at any visit from Week 6 through Week 24 and from Week 24 to Week 48.

To evaluate the safety and tolerability of parsaclisib in participants with wAIHA.	Frequency and severity of AEs, including the evaluation of clinical laboratory results, vital signs, ECGs, and the results of physical examinations.

**Table 1: Objectives and Endpoints (Continued)**

### 3. STUDY DESIGN

[figure not shown]
This is a Phase 3, multicenter, randomized, double-blind, placebo-controlled study to evaluate the efficacy and safety of parsaclisib 2.5 mg QD compared with placebo over a 24-week double-blind treatment period followed by a 24-week open-label treatment period of parsaclisib. Participants may then continue to receive parsaclisib in a long-term extension period.

Participants will receive parsaclisib 2.5 mg QD or matching placebo QD for 24 weeks during the double-blind treatment period. All participants who complete the double-blind treatment period, tolerate study treatment, and (per investigator's opinion) may benefit from treatment, may remain in the study for an additional 24-week, open-label treatment period in which they will receive parsaclisib administered at the same dose and schedule as in the double-blind treatment period.

All participants who complete the open-label treatment period, tolerate study treatment, and (per investigator's opinion) may benefit from continued treatment, may enter into the long-term extension. Parsaclisib will be administered at the same dose and schedule as in the open-label treatment period. During the long-term extension, participants may take a drug holiday one time with the option for re-treatment, should they experience worsening of wAIHA during the drug holiday.

The study schema is shown below in [Figure 1](#). All participants will have follow-up assessments 12 weeks after the last dose of study drug.

**Figure 1:** Study Design Schema

ICF = informed consent form.

a Hemoglobin, at screening, as determined by local laboratory (< 9 g/dL or  $\geq$  9 g/dL) and corticosteroid (prednisone or equivalent) dose at screening ( $\leq$  20 mg/day vs  $>$  20 mg/day).

b The primary analysis will be conducted when the last randomized participant has completed the 24-week, double-blind treatment period.

#### 3.1. Randomization

Approximately 100 participants will be randomized 2:1 to receive initial double-blind study treatment (parsaclisib:matched placebo) for 24 weeks. Participants will be stratified by the hemoglobin value at screening as determined by local laboratory (hemoglobin < 9 g/dL or  $\geq$  9 g/dL) and corticosteroid (prednisone or equivalent) dose at screening ( $\leq$  20 mg/day vs  $>$  20 mg/day).

### **3.2. Control of Type I Error**

For the primary and key secondary endpoints, the overall 2-sided Type I error is 0.05.

The gatekeeping testing strategy for the primary and key secondary analyses will be implemented to control the overall Type I error rate, 2-sided  $\alpha = 0.05$ . The p-value for between-treatment group testing for the primary endpoint will be compared at 2-sided  $\alpha = 0.05$  level. The key secondary endpoint will be tested at 2-sided  $\alpha = 0.05$  level only if the null hypothesis of the primary endpoint is rejected.

### **3.3. Sample Size Consideration**

Approximately 100 participants will be randomized 2:1 (approximately 67:33) to receive either parsaclisib 2.5 mg QD or matching placebo using a fixed block size within each stratum. For the statistical comparison on the binary primary efficacy endpoint, the sample size calculation will be based on a Chi-square test.

Based on the results of the Phase 2 study (INCB 50465-206), the response rate for the primary endpoint is assumed to be 70% for parsaclisib 2.5 mg QD. With limited data, such response rates in the placebo group are not reported in historical studies. The response rate for the placebo group can only be assumed to around 25% from the literature reviewed ([Barcellini et al 2014](#), [Birgens et al 2013](#), [Lechner and Jäger 2010](#)). Based on these assumptions, the sample size of 100 will provide enough power (over 90%) to detect such a difference with a 2-sided alpha of 0.05.

### **3.4. Schedule of Assessments**

Refer to Protocol Amendment 2 dated 10 MAY 2023 for a full description of all procedures and assessment schedules for this study.

## 4. DATA HANDLING DEFINITIONS AND CONVENTIONS

### 4.1. Scheduled Study Evaluations

#### 4.1.1. Day 1

Day 1 is the date that the first dose of study drug is administered to the participants.

#### 4.1.2. Study Day

If a visit/reporting date is on or after Day 1, then the study day at the visit/reporting date will be calculated as follows:

$$\text{Day \#} = (\text{visit/reporting date} - \text{Day 1 date} + 1)$$

If the visit/reporting date is before Day 1, then the study day at the visit/reporting date will be calculated as follows:

$$\text{Day \#} = (\text{visit/reporting date} - \text{Day 1 date})$$

A study day of -1 indicates 1 day before Day 1.

#### 4.1.3. Baseline Value

Baseline is the last nonmissing measurement obtained before the first administration of study drug.

#### 4.1.4. Handling of Missing and Incomplete Data

In general, values for missing data will not be imputed unless methods for handling missing data are specified in this section or relevant sections.

## 4.2. Variable Definitions

### 4.2.1. Body Mass Index

Body mass index will be calculated as follows:

$$\text{BMI (kg/m}^2\text{)} = [\text{weight (kg)}] / [\text{height (m)}]^2$$

### 4.2.2. Prior and Concomitant Medication

Prior medication is defined as any nonstudy medication started before the first dose of study drug. Concomitant medication is defined as any nonstudy medication that is started accordingly:

- Before the date of first dose of study drug and is ongoing throughout the study or ends on/after the date of first study drug administration.
- On/after the date of first dose of study drug and is ongoing or ends during the course of study treatment.

A prior medication could also be classified as "both prior and concomitant medication," if the end date is on or after the first dose of parsaclisib. In the listing, it will be indicated whether a medication is prior-only, concomitant-only, or both prior and concomitant.

For the purposes of analysis, all medications will be considered concomitant medications unless the medications can unequivocally be defined as not concomitant.

## **5. STATISTICAL METHODOLOGY**

### **5.1. General Methodology**

Unless otherwise noted, SAS software (SAS Institute Inc, Cary, NC; v9.1 or later) will be used for the generation of all tables, graphs, and statistical analyses. Descriptive summaries for continuous variables will include, but not be limited to, the number of observations, mean, standard deviation, median, minimum, maximum, first quartile, third quartile, and 95% confidence interval. Descriptive summaries for categorical variables will include the number and percentage of participants in each category.

### **5.2. Treatment Groups**

This is a Phase 3, multicenter, randomized, double-blind, placebo-controlled study to evaluate the efficacy and safety of parsaclisib 2.5 mg QD. Data will be summarized based on the actual treatment that the participant received at Day 1.

Unless other specified, the treatment groups will be parsaclisib 2.5 mg QD and placebo QD. For exposure, compliance, and adverse events, the treatment groups will be placebo QD, placebo QD to parsaclisib 2.5 mg QD, and parsaclisib 2.5 mg QD.

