#### **5.3.1. Safety Population**

All randomized participants who received at least 1 dose of study drug will constitute the safety population. Treatment groups for this population will be determined according to the actual treatment the participant received on Day 1 regardless of assigned study treatment.

All safety and efficacy analyses will be conducted using the safety population.

[REDACTED]

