### 9.1. General Considerations

Analyses in this section will be provided for the safety population. Treatment groups will be provided based on the actual treatment received (see Section 5.2). For participants who cross over treatments, the date of first dose is treatment-specific; the end date will be either 30 days after the date of the last dose of this treatment or the date of the first dose in the next treatment, whichever comes first. Analysis of AEs will be limited to TEAEs, but data listings will include all AEs regardless of their timing in relation to study drug administration. Summary tables may be replaced with listings when appropriate. For instance, an AE frequency table may be replaced with a listing if it only contains a few unique PTs reported on relatively few participants.

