## 9.3. Clinical Laboratory Tests

### 9.3.1. Laboratory Value Definitions

Laboratory values and change from baseline will be summarized descriptively by central laboratory. Baseline will be determined according to Section 4.1.3, with exceptions listed below, in which case the investigative site laboratory or an accredited local laboratory may be used:

- Hematology panels (ie, complete blood count and differential count), will be sent to a local laboratory for analysis.
- Participant management, which includes dose modification, serious adverse event, or COVID-19 restrictions (eg, travel), for local laboratory assessments deemed necessary by the investigator for participant management. Note: Such assessment data and reference ranges must be recorded in the participant's eCRF.

In the event both local and central laboratory assessments are available, local laboratory assessment will be used for analysis. Laboratory values, change from baseline values, and percent change from baseline values will be summarized descriptively by visit. Baseline values will be determined using the nonmissing values collected before the first administration, prioritizing scheduled assessments over unscheduled visits. For baseline laboratory values with the same date and time in the same priority category, additional rules may be provided following consultation with the medical monitor to delineate the value that will be defined as baseline.

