## 9.4. Vital Signs

Descriptive statistics and mean change from baseline will be determined for vital signs (blood pressure, pulse, respiratory rate, and body temperature) at each assessment time.

Criteria for clinically notable vital sign abnormalities are defined in [Table 2](#). The abnormal values for participants exhibiting clinically notable vital sign abnormalities will be listed along with their assigned treatment group. Alert vital signs are defined as an absolute value outside the defined range and percentage change > 25%. The abnormal values for participants exhibiting alert vital sign abnormalities will be listed.

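### Read literally, SAP 5.2 shows labs, vital signs and ECGs taken on parsaclisib after crossover under placebo; SAP 9.1 points the other way, and the text does not say which governs

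*SAP*

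**What the plan says.** SAP 5.2 sets the grouping basis: "Data will be summarized based on the actual treatment that the participant received at Day 1". It names two default groups: "Unless other specified, the treatment groups will be parsaclisib 2.5 mg QD and placebo QD". It then makes one exception: "For exposure, compliance, and adverse events, the treatment groups will be placebo QD, placebo QD to parsaclisib 2.5 mg QD", with parsaclisib from Day 1 as the third group. SAP 5.3.1 repeats the Day 1 rule for the safety population, which is used for every planned table: groups are set "according to the actual treatment the participant received on Day 1 regardless of assigned study treatment".

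For laboratory data, SAP 9.3.1 says: "Laboratory values, change from baseline values, and percent change from baseline values will be summarized descriptively by visit". SAP 9.4 and 9.5 do the same for vital signs and ECGs at each assessment time. None of these three sections limits the summaries to the double-blind period or names a crossover group.

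SAP 9.1 covers all analyses in Section 9: "Treatment groups will be provided based on the actual treatment received (see Section 5.2"). Participants who cross over get a separate first-dose date for each treatment. A treatment's window closes 30 days after its last dose "or the date of the first dose in the next treatment, whichever comes first".

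SAP 9.4 uses a third basis for one listing: "The abnormal values for participants exhibiting clinically notable vital sign abnormalities will be listed along with their assigned treatment group".

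Crossover is part of the design. Under Protocol 4.1, placebo participants who complete 24 weeks may enter open-label parsaclisib. Since Amendment 2 they may start it earlier, in which case they move to the open-label schedule in Protocol Table 4.

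**The concern.** Three bases for grouping stand side by side in the same safety section: Day 1 treatment, actual treatment with treatment-specific windows, and assigned treatment. A programmer who follows SAP 5.2 puts a value measured on parsaclisib in a column headed placebo.

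An example shows what is at stake. Suppose a participant's ALT rises after crossing over from placebo. As an adverse event it is reported under placebo to parsaclisib (SAP Appendix A, Table 3.2.2). As a chemistry value it is reported under placebo (Table 3.3.2). The participant and the period are the same, but the treatment differs. ALT and AST at or above 5 times ULN are events of clinical interest in Protocol 9.6, so readers will look for them in both places. Hemoglobin is affected too, through the hematology summary in Table 3.3.1.

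**Working it through.** **Reading the text.** The plan gives no figure on this point, so the first check sets the rules side by side.

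- If SAP 5.2 governs, labs, vital signs and ECGs fall under its two-group default, because its exception does not name them. Values after crossover then sit under placebo.
- If SAP 9.1 governs, a value after the first parsaclisib dose no longer belongs to placebo. But 9.1 sends the reader back to 5.2 for the groups, and 5.2 defines no crossover group for these data.
- The 9.4 listing follows neither rule, because it uses assigned treatment, which 5.3.1 sets aside.

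**Scheduled assessments per crossover participant.** Inputs are Protocol Table 3 (double-blind) and Table 4 (open-label, through Week 48). Hematology no longer required after Amendment 2 (Weeks 2, 6, 10, 26 and 30) is left out, as are follow-up and long-term extension visits. Each panel or examination counts as one assessment.

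| Assessment | Double-blind, post-baseline | Open-label |
|---|---|---|
| Hematology | Weeks 4, 8, 12, 16, 20, 24 = 6 | Weeks 28, 32, 36, 40, 44, 48 = 6 |
| Chemistry | same weeks = 6 | same weeks = 6 |
| Vital signs | Weeks 2, 4, 6, 8, 10, 12, 16, 20, 24 = 9 | Weeks 26, 28, 30, 32, 36, 40, 44, 48 = 8 |
| ECG | Weeks 12, 24 = 2 | Week 48 = 1 |
| Total | 23 | 21 |

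Share carrying the placebo heading although taken on parsaclisib = on-parsaclisib count / (placebo count + on-parsaclisib count):

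- 24 weeks of placebo, then parsaclisib to Week 48: 21 / (23 + 21) = 21/44 = 48%.
- Crossover after the Week 8 visit (assumed), then the full open-label schedule: placebo count = 2 hematology + 2 chemistry + 4 vital signs + 0 ECG = 8; 21 / (8 + 21) = 21/29 = 72%.
- 24 weeks of placebo, last visit at Week 32 (assumed): on-parsaclisib count = 2 + 2 + 4 = 8; 8 / (23 + 8) = 8/31 = 26%. With an end-of-treatment ECG, 9/32 = 28%.

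These are schedule counts, not observed data. They show how many values would carry the wrong heading, not how far any summary would move.

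**Which rows are affected.** Laboratory summaries are by visit, and vital-sign and ECG summaries are by assessment time. Crossover participants follow Table 4, so most affected values fall in open-label rows, separate from the double-blind rows.

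**Baseline.** SAP 4.1.3 takes the last value before the first study drug. For a participant who starts on placebo, that is a pre-placebo value, and nothing resets it at crossover. Changing the column heading alone therefore leaves open what a change from baseline on parsaclisib is measured from.

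**The case against.** The strongest defence is that the SAP 5.2 default yields wherever something else is specified, and SAP 9.1 does specify something else for all of Section 9. On that reading nothing is mislabelled. A value on parsaclisib could simply go in the existing parsaclisib column, so a third column is not strictly required. This stands in part: mislabelling is not the inevitable result. It does not settle the matter, because 9.1 gives 5.2 as the place where the groups are defined, and 5.2 extends its crossover group to adverse events but not to labs, vital signs or ECGs. Using the parsaclisib column would also differ from the adverse event tables.

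It is also fair that the table shells are in a separate document that was not supplied and may show the intended columns; that some text in 5.3 is redacted; that SAP 9.1 lets listings replace tables; and that SAP 7 and 11.1 rule out p-values and comparisons. The point therefore concerns the SAP wording and descriptive displays only.

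The percentages are open to challenge as well. The 48% and 72% assume that the participant stays to Week 48, yet the sponsor had decided to terminate the study, and Protocol 6.8 offers rollover after 2 months of parsaclisib. Earlier exit gives smaller shares, as the Week 32 case shows.

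**Conclusion.** The wording conflict is real and should be resolved before the tables are programmed. Followed literally, SAP 5.2 and 5.3.1 put on-parsaclisib labs, vital signs and ECGs under placebo; SAP 9.1 points the other way; the text does not say which governs. Up to 21 scheduled assessments per crossover participant are affected through Week 48. The number of participants cannot be computed: SAP 1 gives 13 randomized and dosed, without arm sizes or crossover counts.

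Three stronger readings are not supported:

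- A reader might infer that the double-blind placebo results are contaminated, or that the placebo response rate would drift toward the parsaclisib rate. Crossover participants move to the Table 4 visits, so the error lies mostly in the heading over open-label rows.
- A reader might infer that the SAP certainly mislabels these data. SAP 9.1 can be read as overriding the default, and the shells have not been seen.
- A reader might infer that SAP 7.2 admits open-label visits to the primary endpoint, because it summarizes visits after baseline by Day 1 treatment without a period limit. SAP Table 1 still confines that endpoint to the 24-week double-blind period, 7.2 keeps the word durable, and the key secondary endpoint is fixed at Week 24. This is a shortened restatement, not a changed endpoint.

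**What to change.** 1. In SAP 5.2, extend the existing three-group rule to laboratory, vital-sign and ECG data, and tie it to the SAP 9.1 treatment windows. Values after the first parsaclisib dose in a participant who started on placebo then appear under placebo to parsaclisib, as in the adverse event tables.
2. In the SAP 9.4 listing, use the same grouping in place of assigned treatment.
3. State which baseline applies to change values after crossover, since SAP 4.1.3 as written gives the pre-placebo value.
4. As a wording alignment only, repeat Table 1's durable criterion and double-blind limit in SAP 7.2 and in the Table 2.1.1 title.

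The cost is a few sentences of SAP text and minor reprogramming; SAP 9.1 already requires a first-dose date for each treatment. The downside is one more column in already small tables and fewer observations in the placebo column.

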### **5.3. Analysis Populations**

Upon implementation of Protocol Amendment 2, enrollment closed and Protocol-required procedures have been reduced for ongoing participants. With limited participants enrolled in each treatment group, as well as the option for early crossover to parsaclisib, the statistical analyses, as defined by the Protocol, will not be applicable; as a result, only the safety population [REDACTED] will be used for analysis.

#### **5.3.1. Safety Population**

All randomized participants who received at least 1 dose of study drug will constitute the safety population. Treatment groups for this population will be determined according to the actual treatment the participant received on Day 1 regardless of assigned study treatment.

All safety and efficacy analyses will be conducted using the safety population.

[REDACTED]

